## Pregnancy

Any pregnancy that occurs in a female partner of a male study participant should be reported to the Overall PI. Information on this pregnancy will be collected on the BMS Pregnancy Surveillance Form. Follow-up information regarding the course of the pregnancy, including perinatal and neonatal outcome and, where applicable, offspring information must be reported on the Pregnancy Surveillance Form. Please contact the Research Project Manager if you do not have this form in your regulatory files.

Pregnancies and suspected pregnancies (including a positive pregnancy test regardless of age or disease state) of a female subject occurring while the subject is on lenalidomide, or within 28

CONFIDENTIAL

This document is confidential. Do not disclose or use except as authorized.

days of the subject's last dose of lenalidomide, are considered immediately reportable events. Lenalidomide is to be discontinued immediately. The pregnancy, suspected pregnancy, or positive pregnancy test must be reported to Celgene Drug Safety immediately by facsimile or email using the Pregnancy Initial Report Form. The female subject should be referred to an obstetrician-gynecologist, preferably one experienced in reproductive toxicity for further evaluation and counseling.

The Investigator will follow the female subject until completion of the pregnancy, and must notify Celgene Drug Safety immediately about the outcome of the pregnancy (either normal or abnormal outcome) using the Pregnancy Follow-up Report Form. If the outcome of the pregnancy was abnormal (e.g., spontaneous or therapeutic abortion), the Investigator should report the abnormal outcome as an AE. If the abnormal outcome meets any of the serious criteria, it must be reported as an SAE to Celgene Drug Safety immediately by facsimile, or other appropriate method, within 24 hours of the Investigator's knowledge of the event using the SAE Report Form.

All neonatal deaths that occur within 28 days of birth should be reported, without regard to causality, as SAEs. In addition, any infant death after 28 days that the Investigator suspects is related to the in utero exposure to the IP should also be reported to Celgene Drug Safety immediately by facsimile, or other appropriate method, within 24 hours of the Investigator's knowledge of the event using the SAE Report Form.

#### Male Subjects

If a female partner of a male subject taking investigational product becomes pregnant, the male subject taking lenalidomide should notify the Investigator, and the pregnant female partner should be advised to call their healthcare provider immediately.

#### **Overdose**

Include any product-specific definition of overdose in addition to the following mandatory statement as the last sentence.

An overdose is defined as the accidental or intentional administration of any dose of a product that is considered both excessive and medically important. All occurrences of overdose must be reported as SAEs.

CONFIDENTIAL

This document is confidential. Do not disclose or use except as authorized.

## **Overdose of Lenalidomide**

Overdose, as defined for this protocol, refers to Revlimid dosing only.

On a per dose basis, an overdose is defined as the following amount over the protocol-specified dose of Revlimid assigned to a given patient, regardless of any associated adverse events or sequelae.

- PO any amount over the protocol-specified dose

On a schedule or frequency basis, an overdose is defined as anything more frequent than the protocol required schedule or frequency.

Complete data about drug administration, including any overdose, regardless of whether the overdose was accidental or intentional, should be reported in the case report form.

### **7.4.1 Protocol-Specific Expedited Adverse Event Reporting Exclusions**

There are no protocol specific exclusions.

## **7.5 Expedited Reporting to the Food and Drug Administration (FDA)**

The Overall PI, as study sponsor, will be responsible for all communications with the FDA. The Overall PI will report to the FDA, regardless of the site of occurrence, any serious adverse event that meets the FDA's criteria for expedited reporting following the reporting requirements and timelines set by the FDA.

## **7.6 Expedited Reporting to Bristol-Myers Squibb (BMS)**

The Overall PI, as study sponsor, will be responsible for all communications with the BMS. With the exception of any serious adverse event that meets the FDA's criteria for expedited reporting following the reporting requirements and timelines set by the FDA. All SAEs and SUSARs should simultaneously be faxed or e-mailed to BMS by each participating site at:

Global Pharmacovigilance & Epidemiology  
Bristol-Myers Squibb Company  
[contact]  
Email: [[contact]](mailto:[contact])

The written report must be completed and supplied to BMS by facsimile or e-mail within 3 business days. The report should also include the BMS trial number, which is CA204-119.

## **7.7 Expedited Reporting to Celgene**

Serious adverse events (SAE) are defined above. The investigator must inform Celgene in writing using a Celgene SAE form or MEDWATCH 3500A form of any SAE within 24 hours of

CONFIDENTIAL

This document is confidential. Do not disclose or use except as authorized.

being aware of the event. The written report must be completed and supplied to Celgene by facsimile within 24 hours. The initial report must be as complete as possible, including an assessment of the causal relationship between the event and the investigational product(s). Information not available at the time of the initial report (e.g., an end date for the adverse event or laboratory values received after the report) must be documented on a follow-up report. A final report to document resolution of the SAE is required. The Celgene tracking number (RV-CL-MM-PI-004473) and the institutional protocol number should be included on SAE reports (or on the fax cover letter) sent to Celgene. A copy of the fax transmission confirmation of the SAE report to Celgene should be attached to the SAE and retained with the patient records.

## 7.8 Expedited Reporting to Hospital Risk Management

Participating investigators will report to their local Risk Management office any participant safety reports or sentinel events that require reporting according to institutional policy.

## 7.9 Routine Adverse Event Reporting

All Adverse Events **must** be reported in routine study data submissions to the Overall PI on the toxicity case report forms. **AEs reported through expedited processes (e.g., reported to the IRB, FDA, etc.) must also be reported in routine study data submissions.**

## 8. PHARMACEUTICAL INFORMATION

A list of the adverse events and potential risks associated with the Elotuzumab and lenalidomide administered in this study can be found in Section 7.

### 8.1 Elotuzumab

#### 8.1.1 Description

Elotuzumab (BMS- 901608; formerly known as HuLuc63) is a humanized recombinant monoclonal IgG1 antibody product directed to human SLAMF7 (CD2-subset-1, also known as CRACC), a cell surface glycoprotein that is highly expressed in MM cells.

#### 8.1.2 Form

Elotuzumab for injection has been developed to be used as an intravenous (IV) infusion for the clinical studies. Drug product is a non-pyrogenic lyophilized powder which is white to off-white contained in 20-cc Type I glass vials, closed with 20-mm stoppers and sealed with aluminum seals. Each vial of drug product contains the labeled amount of BMS-901608 drug substance, sucrose, sodium citrate dihydrate, citric acid, and polysorbate 80. A 10% overfill is included in each vial to account for vial, needle, syringe (VNS) holdup. The drug product will be reconstituted prior to administration.

**Table 7**

Product	Potency	Primary	Secondary	Appearance	Storage
---------	---------	---------	-----------	------------	---------

CONFIDENTIAL

This document is confidential. Do not disclose or use except as authorized.

Description and Dosage Form		Packaging (Volume)/Label Type	Packaging (Qty) /Label Type		Conditions (per label)
Elotuzumab Powder for Solution for Infusion	400mg/vial	20 ml vial/ open Label	10 vials per kit/open Label	Sterile, white to off-white, preservative-free, lyophilized cake	Store at 2°C - 8°C

#### 8.1.3 Storage and Stability

The product storage manager should ensure that the study drug is stored in accordance with the environmental conditions (temperature, light, and humidity) as determined by the sponsor. If concerns regarding the quality or appearance of the study drug arise, do not dispense the study drug and contact the sponsor immediately.

The lyophilized elotuzumab drug product should be stored at 2° to 8° C. Prior to administration the drug product must be reconstituted with Sterile Water for Injection, USP, and then further diluted in 0.9% sodium chloride normal saline, USP, as per the instructions in Appendix B. After the dose is diluted in normal saline, it must be administered within 8 hours if stored at room temperature. If a delay is anticipated, the prepared dose may be refrigerated at 2° to 8° C for up to 24 hours. If stored under refrigerated conditions, the prepared study drug solution should be equilibrated to room temperature (process takes 2 - 2.5 hours) and the container must be gently inverted to mix well before administration. Do not use the accelerated warming method. If administration is delayed beyond the specified time, the prepared dose solution must be discarded, and the reason documented by the pharmacist in study drug accountability records. The dose of elotuzumab to be administered to a subject will be calculated by multiplying the subject's weight (kg) by 10 mg/kg. The subject's predose weight on Day 1 of each cycle or predose weight at each visit, whichever is institutional policy, will be used to calculate the dose for each cycle. Each dose should be infused as per instructions in Appendix B.

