**Elotuzumab and Lenalidomide Maintenance Therapy (Cycles 9-24)**

Agent	Premedication and Precautions	Schedule	Dose	Route	Cycle Length
Elotuzumab	Premedications are described below	Days 1 of each cycle	20 mg/kg	Intravenous-See appendix B for more details	
Lenalidomide	None	Days 1-21 of each cycle	15 mg	Oral	28 days (4 weeks)
Dexamethasone*	Take with food; recommended to be taken in the morning	Day 1 of each cycle	8 mg	IV	
			28 mg	Oral	

\* After discussion with the overall PI, high-dose dexamethasone may be re-added during maintenance due to biochemical progression (progressive increase in SPEP [25% and an absolute increase of 0.5g/d] or UPEP [25% and an absolute increase of 200mg/24hours] on 2 successive evaluations as determined by the IMWG response criteria or documented progression by the FreeLite™ progressive disease criteria in the absence of serum or urine involvement). Dexamethasone should be given as follows after overall PI approval:

Day	Dose	Route
1	8 mg	IV
	32 mg	Oral
8	40 mg	Oral
15	40 mg	Oral

CONFIDENTIAL

This document is confidential. Do not disclose or use except as authorized.

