#### 5.3.1 Elotuzumab

Elotuzumab will be administered intravenously at a dose of 10 mg/kg on Days 1, 8, 15 and 22 for the first 2 cycles (a cycle =28 days). During cycles 3 through 8, elotuzumab will be given on days 1 and 15. Elotuzumab will be administered intravenously at a dose of 20 mg/kg only on Day 1 for cycles 9-24. The patient should be observed for 60 minutes after the infusion is complete for cycle 1 and should be observed for 30 minutes after the infusion for subsequent cycles. All patients should have their vital signs checked before and after elotuzumab infusion or per institutional standard. If an infusion reaction occurs, reference section 6.4.2 for guidelines on additional vital monitoring.

Cycle 1 and Cycle 2 treatment may be administered +/- 3 days. For subsequent cycles +/- 7 days is allowed.

CONFIDENTIAL

This document is confidential. Do not disclose or use except as authorized.

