#### 8.1.7 Administration

Elotuzumab will be given cycle 1 & 2 at 10 mg/kg IV once a week (days, 1, 8, 15, and 22).  
Elotuzumab will be given cycle 3 to 8 at 10mg/kg IV days 1 and 15 every cycle.  
Maintenance elotuzumab will be given at 20 mg/kg IV day 1 every cycle up to cycle 24 (total of 2 years).

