## APPENDIX B: PREPARATION AND ADMINISTRATION OF ELOTUZUMAB

### Dose Preparation Instructions

After dilution in normal saline, elotuzumab must be administered within 8 hours if kept at room temperature (25°C). If a delay is anticipated after the dose has been diluted in normal saline, the prepared dose (properly identified) may be refrigerated at 2°C to 8°C for up to 24 hours. If stored under refrigerated conditions, the study drug solution should be equilibrated to room temperature (takes about 2 to 2.5 hours), and the container must be gently inverted to thoroughly mix the contents before administration. If the storage time limit is exceeded, the prepared dose solution must be discarded and the reason documented by the pharmacist in the study drug accountability records.

Elotuzumab will be administered to each subject as an IV infusion, using an automated infusion pump set at the appropriate rate according to the dose administration section (see Administration Instruction section below) discussed below. The dose of elotuzumab will be calculated using the subject's predose weight on Day 1 of each cycle or predose weight at each visit, whichever institutional policy is, and then added to 0.9% saline for infusion. Do not round up or down.

Reconstitute elotuzumab lyophilized study drug, as described in Steps 1 to 5. Each 400 mg vial contains 10% overfill for a total of 440 mg of study drug but is intended to deliver 400 mg of elotuzumab. Standard aseptic technique should be utilized.

Step 1: Remove the flip-top from elotuzumab and Sterile Water for Injection (SWFI) vials.

Step 2: Withdraw 17 mL of SWFI using an 18-gauge or smaller needle. Place the elotuzumab vial upright on a flat surface and insert the syringe needle into the vial through the center of the rubber stopper. Slowly inject the SWFI along the side of the vial to help prevent bubbling or foaming. Slowly remove the syringe needle out of the vial.

Step 3: DO NOT SHAKE. Avoid prolonged or vigorous agitation. Hold the vial upright and gently swirl the solution by rotating the vial to dissolve the lyophilized cake. Then gently invert the vial a few times in order to dissolve any powder that may be present on top of the vial or the stopper. Finally, hold the vial upright again and gently swirl the solution a few more times to dissolve any remaining particles.

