Step 4: After the remaining solids are completely dissolved, allow the reconstituted solution to stand for 5 to 10 minutes. The final volume of the reconstituted solution is approximately 17.6 mL, for an approximate concentration of 25 mg/mL.

It is acceptable to have small bubbles and/or foam around the edge of the vial. The reconstituted preparation results in a colorless to slightly yellow, clear to slightly opalescent solution.

Step 5: Once the reconstitution is completed and prior to IV administration, the reconstituted solution is further diluted with 230-340 ml of 0.9% sodium chloride injection (NS), USP, resulting in elotuzumab concentrations between 2 mg/mL and 6.6 mg/mL. The infusion is to be administered through a sterile, non-pyrogenic, low protein binding in-line filter. Additionally,

CONFIDENTIAL

This document is confidential. Do not disclose or use except as authorized.

care must be taken to ensure the sterility of the prepared solution, as the drug product does not contain anti-microbial preservatives or bacteriostatic agents. A sufficient excess of drug product is included in each vial to account for withdrawal losses.

The first dose of elotuzumab will be administered following pre-medications to each subject as an IV infusion, using an automated infusion pump set at an initial rate of 0.5 mL per minute (30 mL/hour). If the subject does not have an infusion reaction within 30 minutes, escalate the infusion rate by 0.5 mL per minute. If the subject still does not have an infusion reaction within 30 minutes, escalate the infusion rate to a maximum of 2 mL per minute (120 mL/hour). If a subject experiences a Grade 2 infusion reaction, the infusion must be interrupted.

The second dose of elotuzumab should be initiated at an infusion rate of 3 mL per minute if no infusion reactions were reported with the first elotuzumab infusion. If the subject does not experience an infusion reaction during the first 30 minutes of the second dose of elotuzumab, escalate the infusion rate by 1.0 mL per minute to a maximum infusion rate of 4 mL per minute.

If no infusion reactions were observed during the first two doses cycle of elotuzumab, the third dose can commence at a rate of 5 mL per minute.

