**Note: Subjects must be premedicated as described previously prior to elotuzumab infusion.**

The elotuzumab infusion rate will be increased gradually to a maximum of 5 mL/min as presented in the table below. The schedule below will be permitted only if no infusion reactions are encountered. For guidance related to elotuzumab infusion reactions, refer to section 6.4.

Cycle/Day	Infusion Rate	Duration of Infusion	Approximate Total Infusion Time
Cycle 1 Day 1 (10mg/kg)	0.5 mL/min	30 minutes	2 hours and 50 minutes
	1 mL/min	30 minutes	
	2mL/min	110 minutes	
Cycle 1 Day 8 (10mg/kg)	3 mL/min	30 minutes	1 hour and 13 minutes
	4 mL/min	43 minutes	
Cycle 1 Day 15 and 22 And Cycle 2-8 (10mg/kg)	5mL/min	53 minutes	53 minutes
Cycle 9-24 (20mg/kg)	5mL/min	81 minutes	81 minutes

CONFIDENTIAL

This document is confidential. Do not disclose or use except as authorized.

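### Section 8.1.3 sets the elotuzumab dose at 10 mg/kg in every cycle although cycles 9-24 are 20 mg/kg, and three rows of the 6.2 table say off-study where they should say off protocol therapy

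*Combined protocol and SAP*

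**What the plan says.** **Dose.** Section 8.1.3 (Storage and Stability) says the elotuzumab dose is "calculated by multiplying the subject's weight (kg) by 10 mg/kg". Its next sentence says the patient's weight "will be used to calculate the dose for each cycle". Neither sentence limits the rule to particular cycles. Section 5.3.1 says "Elotuzumab will be administered intravenously at a dose of 20 mg/kg only on Day 1 for cycles 9-24". The maintenance table in 5.1, section 8.1.7 and the cycle 9-24 row of the Appendix B rate table also give 20 mg/kg. The preparation text in Appendix B says "The dose of elotuzumab will be calculated using the subject's predose weight on Day 1 of each cycle" (or at each visit, by local policy) and states no mg/kg figure. Section 2.9 describes the dose in this study as 10 mg/kg per cycle, again without qualification.

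**Off-study rows.** In the 6.2 non-hematologic table, both infection rows (ANC at least 1000 and ANC below 1000) and the Grade 4 row for other related toxicities require a patient with a delay of more than 21 days to come off study. Section 5.7 gives four reasons for going off study: loss to follow-up, completion of 3 years of follow-up, withdrawal of consent for data submission, and death. Section 5.6 follows patients for up to 3 years after removal from protocol therapy, or until symptomatic myeloma. Section 6.4.2 uses the term off protocol therapy for a patient who stops elotuzumab before the end of cycle 2.

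**The concern.** Both sentences are instructions that sites act on, and each conflicts with the rest of the protocol.

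The dose rule sits among preparation and pharmacy-record instructions, so its likely readers are the people who prepare the drug. Applied in maintenance, it gives half the intended dose. Section 6.1 allows no elotuzumab dose reduction, so this would also be an unplanned departure from protocol.

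The off-study wording bears on the primary endpoint. A patient who leaves the study is no longer assessed for progression, and 13.1.1 censors at the date last known progression-free. Patients removed this way would be selected by infection or severe toxicity. Twenty-four cycles of 28 days are 672 days, so without earlier delays any removal during treatment comes before the 2-year mark.

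**Working it through.** **Dose, inputs** (5.1, 5.3.1, 8.1.7): cycles 1-2, 10 mg/kg on 4 days per cycle; cycles 3-8, 10 mg/kg on 2 days; cycles 9-24 (16 cycles), 20 mg/kg on 1 day.

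- Planned total: 2 × 4 × 10 + 6 × 2 × 10 + 16 × 20 = 80 + 120 + 320 = 520 mg/kg.
- With 8.1.3 applied throughout: 80 + 120 + 16 × 10 = 80 + 120 + 160 = 360 mg/kg.
- Difference: 160/320 = 50% less in maintenance; (520 − 360)/520 = 30.8% less overall.
- At an assumed 80 kg, each maintenance dose would be 800 mg (two 400 mg vials) instead of 1600 mg (four vials).

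**Which figure is intended.** Four places state 20 mg/kg for maintenance. The infusion time in Appendix B agrees with them, though the table already prints the dose, so this only supports the reading. Appendix B says "the reconstituted solution is further diluted with 230-340 ml of 0.9% sodium chloride injection (NS), USP", at about 25 mg/mL after reconstitution, and gives 81 minutes at 5 mL/min for cycles 9-24. That is 405 mL. Taking the upper diluent volume (340 mL, my choice within the stated range) and 80 kg:

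- 20 mg/kg: 1600/25 = 64 mL; 64 + 340 = 404 mL; 404/5 = 80.8 min (77.6 to 84.0 min for 60 to 100 kg).
- 10 mg/kg: 800/25 = 32 mL; 32 + 340 = 372 mL; 372/5 = 74.4 min (72.8 to 76.0 min for 60 to 100 kg).

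**Section 2.9.** Per-cycle doses from the schedule are 4 × 10 = 40 mg/kg (cycles 1-2), 2 × 10 = 20 mg/kg (cycles 3-8) and 1 × 20 = 20 mg/kg (cycles 9-24). No block gives 10 mg/kg per cycle. That figure would arise only in maintenance dosed by the 8.1.3 rule, so a reader who checks 8.1.3 against 2.9 could take the error as confirmed.

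**Off-study rows, side by side.**

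- 6.2 table, three rows: delay over 21 days leads to off study.
- 5.7: four off-study reasons, and a treatment delay is not one of them.
- 5.6: follow-up continues after removal from protocol therapy, which is the status these patients would otherwise have.
- 6.4.2: the same part of the protocol uses the narrower term where therapy alone stops.

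Taken at their word, the three rows and sections 5.6 and 5.7 cannot all be followed.

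**Design figures, for context.** The rule of 24 or more of 39 gives P(X ≥ 24 | n = 39, p = 0.50) = 0.0998 and P(X ≥ 24 | n = 39, p = 0.70) = 0.906. Section 13.1 states 0.10 and above 0.9. The stated figures reproduce, and neither wording error enters them.

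**The case against.** **The dose is settled elsewhere.** Sections 5.1, 5.3.1 and 8.1.7 govern dosing, and all say 20 mg/kg. Section 8.1.3 itself sends the reader to Appendix B for the infusion, where the rate table prints 20 mg/kg for cycles 9-24. This stands. A reader might infer that the maintenance dose is undetermined, or that patients will receive 31% less drug. The documents do not support either: the 31% arises only if one sentence in a storage section overrides four others for 16 cycles. It measures a literal misreading and is not an expected effect.

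**Off-study is loose wording.** Sections 5.5, 6.1 and 6.3 use on study to mean on treatment, and 5.5 and 5.7 each require their own reason and date in the case report form, so the two statuses are recorded separately. This also largely stands, and off protocol therapy is probably what the rows mean. It does not make the wording right. Section 5.7 defines off study as a distinct status, and the form that 5.5 requires on removal from therapy carries both terms in its title.

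**The 21-day limit.** A reader might infer that the rows are also wrong to set a firm limit, because the opening of 6.2 allows longer lenalidomide holds with overall PI approval. The text is divided on this: 6.1 gives a 21-day maximum, and 6.2 gives it twice more. The rows agree with those statements, so the limit cannot be called their error.

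**Conclusion.** Both are minor consistency errors in operative text, and both are wrong as written. Following 8.1.3 literally in cycles 9-24 gives 160 instead of 320 mg/kg in maintenance and 360 instead of 520 mg/kg in total, assuming all 24 cycles are given on schedule. This would be under-dosing; no toxicity concern follows from it.

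The off-study rows, read literally, end progression follow-up and lead to early censoring in the 2-year Kaplan-Meier estimate. A reader might infer a biased primary result or lost power. The documents do not support that: they give no rate of delays over 21 days and nothing that links such delays to progression, so no size can be attached. Alpha, power and the planned analysis are unaffected.

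**What to change.** - In 8.1.3, state the dose as 10 mg/kg for cycles 1-8 and 20 mg/kg for cycles 9-24.
- In 2.9, align the 10 mg/kg per cycle sentence with the schedule in 5.1.
- In the three rows of the 6.2 non-hematologic table, replace off-study with: off protocol therapy, and continues follow-up per 5.6. Add no PI-approval exception there, since that would loosen a stopping rule.
- Separately, the sponsor should decide whether holds over 21 days are allowed, and make 6.1 and 6.2 agree.

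The wording changes fit in one clarifying amendment with a notice to sites. They need no new procedures, visits or patients.
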